## SCHEMA

### Phase I Dose Escalation

#### Phase I: 3 + 3 dose escalation

### Phase II

[figure not shown]
#### CLL/SLL Cohort

CONFIDENTIAL

This document is confidential. Do not disclose or use except as authorized.

**Stage I:** Enroll 12 CLL/SLL patients

**Stage II:** If at least 2 CLL/SLL patients achieve a complete response (CR) as defined by the IWCLL 2008 criteria after one year, an additional 23 patients will be enrolled in the second stage.

**RS Cohort**

Twenty patients with RS will be enrolled to a separate phase II cohort and treated with the same regimen as above for the phase II CLL/SLL Cohort.

CONFIDENTIAL

This document is confidential. Do not disclose or use except as authorized.

## SYNOPSIS

Title of Study: A Phase I/II Study of Duvelisib and Venetoclax in Patients with Relapsed or Refractory Chronic Lymphocytic Leukemia, Small Lymphocytic Lymphoma, or patients with Richter's Syndrome

Principal Investigator: [name], MMSc

Study Center(s): This study will be conducted within the Dana-Farber/Harvard Cancer Center (Dana-Farber Cancer Institute and Massachusetts General Hospital. Collaborator includes [name] (MGH).


Rationale:
 
Venetoclax, a potent, selective inhibitor of BCL-2, was approved by the U.S. Food and Drug Administration (FDA) in 2016 for the treatment of relapsed/refractory chronic lymphocytic leukemia (CLL) with deletion 17p (del(17p)). Venetoclax has since been established as an effective therapeutic option for patients with traditionally difficult to treat disease. While venetoclax has demonstrated impressive clinical results, complete response (CR) rates range from only 10-20% as monotherapy, and responses are not durable for many patients. In the initial phase I trial, 35% of patients progressed within 15 months of initiating therapy. Based on experience with chemoimmunotherapy, achieving a CR with minimal residual disease (MRD) negativity is highly beneficial both in terms of remission duration and overall survival (OS). Novel therapeutic strategies, especially those utilizing combination approaches, are urgently needed, as they have the potential to deepen responses and thus improve outcomes for patients with relapsed/refractory CLL.
 
Duvelisib, an oral, reversible and selective small molecule dual inhibitor of PI3K-<math>\delta</math> and PI3K-<math>\gamma</math>, has emerged as a promising therapeutic option for patients with CLL. Preclinical studies have shown that duvelisib inhibits B-cell receptor (BCR) signaling, reduces chemotaxis, and inhibits cytokine mediated CLL cell proliferation. PI3K-<math>\gamma</math> inhibition also inhibits the tumor-promoting effects of T-cells and myeloid cells in the microenvironment, providing the potential for enhanced anti-tumor effect as compared to PI3K-<math>\delta</math> inhibition alone. At concentrations achieved at a dose of 25 mg BID, duvelisib results in near complete inhibition of PI3K-<math>\delta</math> and fifty percent inhibition of PI3K-<math>\gamma</math>. Early phase clinical trials have shown overall response rates in relapsed/refractory CLL in the 80% range with a manageable toxicity profile at this dose, making this a suitable partner for combination studies. Duvelisib was FDA-approved in 2018 for patients with relapsed/refractory CLL after 2 or more prior therapies.
 
As venetoclax and duvelisib target pathways fundamental to CLL biology and have distinct mechanisms of action, they offer great promise as a combination therapy for the treatment of patients with CLL. Preclinical data further supports this combination, as duvelisib therapy has been shown to upregulate BCL-2 transcript and protein expression levels and enhance the ability of venetoclax to induce apoptosis in ex vivo human CLL cells. BH3 profiling has also


CONFIDENTIAL

This document is confidential. Do not disclose or use except as authorized.

previously shown that inhibition of PI3K enhances the apoptotic threshold of CLL cells and sensitivity to BCL-2 inhibition.

**Study Concept:**

In this phase I/II trial, we combine duvelisib and venetoclax in patients with relapsed/refractory CLL, small lymphocytic lymphoma (SLL), or Richter's Syndrome (RS). We aim to determine the maximum tolerated dose (MTD) of venetoclax to be used in combination with duvelisib and the safety of combination therapy. We will also monitor for MRD. Patients achieving MRD negativity have the option to discontinue therapy after at least one year of treatment, which has the potential to reduce the toxicities associated with indefinite treatment, improve adherence to therapy, and significantly reduce costs.

In correlative laboratory studies, we will utilize BH3 profiling, a functional assay that determines the apoptotic threshold of a cell, to determine whether duvelisib primes cells for death or enhances their reliance on BCL-2 for survival. This has the potential to predict response and identify patients likely to benefit from combination therapy. We can also use this tool to identify whether the dependence on other anti-apoptotic proteins, such as MCL-1 or BCL-XL, confers resistance to therapy. Given the effects of PI3K inhibition on T-cells and myeloid cells in the microenvironment, we also plan to use cytometry by time-of-flight (CyTOF) to identify the effect of duvelisib on immune subsets and determine how this impacts response to therapy as well as toxicity.

**Primary Objectives:**

**Phase I:**

- Determine the dose limiting toxicities (DLTs), and the maximum tolerated dose (MTD) as well as the recommended phase II dose for this combination regimen of duvelisib plus venetoclax for patients with relapsed or refractory CLL/SLL

**Phase II:**

- Determine the rate of complete response (CR) of duvelisib in combination with the MTD of venetoclax, as defined by the IWCLL 2008 criteria for CLL/SLL or Lugano 2014 Criteria for RS

**Secondary Objectives:**

**Phase I:**

- Evaluate pharmacokinetics of both duvelisib and venetoclax in patients with CLL/SLL and with RS

**Phase II:**

- Evaluate preliminary efficacy, including objective response rate (ORR), duration of response (DOR) among patients who have achieved a partial response (PR) or CR, progression free survival (PFS), and OS in patients treated with combined duvelisib and venetoclax
- Determine the rate of MRD negativity (MRD-negative CR) in the bone marrow after six months and one year of combination therapy

CONFIDENTIAL

This document is confidential. Do not disclose or use except as authorized.

- Determine the association of FISH abnormalities, *TP53*, *NOTCH1*, or *SF3B1* mutations, complex karyotype, and *IGHV* mutational status with ORR, CR rate, and PFS
- Evaluate pharmacokinetics of both duvelisib and venetoclax in patients with RS

#### **Exploratory Objectives:**

- Use both standard (performed prior to initiation of therapy and following one week of duvelisib monotherapy) and dynamic BH3 profiling to determine whether duvelisib therapy enhances mitochondrial priming and how this correlates with response
- Use BH3 profiling (performed prior to initiation of therapy, following one week of duvelisib monotherapy, and after three and six months of combination therapy) to determine whether dependency of anti-apoptotic proteins other than BCL-2 (i.e. MCL-1 and BCL-XL) predicts resistance to therapy
- Use CyTOF to identify how duvelisib monotherapy and duvelisib and venetoclax combination therapy impacts immune cell subtypes, in particular the ratio of regulatory to conventional T cells, and how this correlates with response and toxicity
- Determine change in lymph node size following one week of duvelisib monotherapy
- Determine change in quality of life score using quality of life survey (appendix F) after one week of duvelisib monotherapy

**Study Design:** This is an open-label, multicenter, phase I/II study of duvelisib in combination with venetoclax for patients with relapsed/refractory CLL/SLL or patients with Richter's Syndrome (RS) of any disease status

#### ***Phase I:***

In the phase I study, patients will start with 25 mg BID of duvelisib for seven days. A traditional 3 + 3 design will be used to accrue patients to one of three doses of venetoclax, which will start on day 8 and will be given in combination with duvelisib. The starting dose level of venetoclax will be 100 mg daily (dose level +1) with escalation to 200 mg daily (dose level +2) and to 400 mg daily (dose level +3). De-escalation to 50 mg daily (dose level -1) will be performed if unexpected toxicity is observed.

At each dose level, patients will undergo a weekly dose ramp-up of venetoclax starting with a dose of 10 mg (given the potential for drug-drug interactions), and subsequently ramp-up to the eventual cohort dose. Patients in the initial dosing cohorts will stop at a lower dose of venetoclax than the approved dose of 400 mg. Patients will be admitted for each dose of venetoclax during the dose ramp-up for close monitoring for tumor lysis syndrome (TLS). Patients will continue combination therapy for up to one year. Once the MTD of venetoclax in combination with duvelisib is determined, patients assigned to lower dose levels in the phase I trial will also have the option to escalate their venetoclax dose to the MTD.

#### ***Phase II:***

The phase II study will include two stages. We will start by enrolling 12 CLL/SLL patients who will receive 25 mg BID of duvelisib followed by venetoclax. If 2 CLL/SLL patients

CONFIDENTIAL

This document is confidential. Do not disclose or use except as authorized.

achieve a CR after one year of therapy, an additional 23 CLL/SLL patients will be enrolled in the second stage. A separate cohort of 20 patients with Richter's Syndrome will be enrolled in parallel with the CLL/SLL cohort in a one stage design.

Since no TLS was observed with the 10 mg starting dose of venetoclax in phase I, patients in the phase II portion of the study start will have the option to start with 10 or 20 mg of venetoclax as per the standard of care and will follow a standard dose ramp-up to the MTD. Patients who are low- or medium risk for TLS and wish to be treated all in the outpatient setting will have to start at 10 mg and then the following week go up to 20 mg, and then complete the rest of the usual ramp-up to 50 mg, 100 mg, 200 mg, and 400 mg. High risk patients will all be hospitalized for the initial dose ramp-ups, and will have the option to start at 10 or 20 mg. If they start at 10 mg, they will need to be hospitalized for the first 3 dose ramp-ups (10 mg, 20 mg, and 50 mg), or first 2 dose ramp-ups (20 and 50mg) if they start at 20 mg. When venetoclax dosing is performed as an outpatient, TLS labs should be checked pre-dose, approximately 6-8 hours after first dose and approximately 24 hours after treatment.

Accelerated ramp up for RS patients: Given the potential for rapidly progressive RS, these patients will also have the option to undergo an accelerated venetoclax ramp-up in the inpatient setting modeled after another study of venetoclax plus chemotherapy that was recently reported ([name] et al., ICML, 2019). In that study, venetoclax was safely ramped up in a daily fashion for 20 RS patients, who were monitored closely in the inpatient setting, with no evidence of tumor lysis syndrome. The venetoclax is dosed at 20mg for day 1, and if no TLS is observed on labs done 6-8 hours and 24 hours later, then the dose is ramped up to 50mg on day 2, 100mg on day 3, 200mg on day 4, and 400mg on day 5 if the daily labs done 6-8 hours and 24 hours later continue to show no TLS. If laboratory TLS does occur, the next day's dose will be held until there is improvement in the TLS, at which point escalation to the next dose may occur

Study visits will occur weekly through cycles 1-2, once per cycle during cycles 3-7, every 2 cycles from cycle 8-13, then every 3 cycles up to cycle 60, and then every 6 cycles thereafter until discontinuation of therapy. Patients will be treated with duvelisib plus venetoclax combination therapy for up to one year (12 cycles), followed by venetoclax monotherapy until the time of disease progression without clinical benefit, death, unacceptable toxicity, withdrawal of consent.

Additionally, if after at least one year of combination treatment, a patient achieves a complete remission (CR) or complete remission with incomplete count recovery (CRi) with MRD-negativity in the bone marrow, they will have the option to discontinue therapy. Those that come off treatment for this reason will be monitored for disease recurrence with peripheral blood MRD testing by flow cytometry approximately every 3 months. Patients who have detectable recurrence (at minimum, confirmed by two successive peripheral blood MRD positive assessments) in the peripheral blood will have the option to restart venetoclax. If they do not achieve MRD negativity or have evidence of disease progression after reaching

CONFIDENTIAL

This document is confidential. Do not disclose or use except as authorized.

full dose venetoclax monotherapy, they will also have the option to add duvelisib and continue it until MRD negativity is achieved on two successive peripheral blood MRD assessments or indefinitely depending on tolerability.

CT scans (or PET/CT for Richter's participants) will occur at C4, C7, C13. After this first year, scans can be done every 6 cycles thereafter, or at the investigator's discretion. Bone marrow biopsies and aspirates will be mandatory at study entry (unless within screening window), at the C7D1, C13D1, and C25D1 re-staging visits and as clinically indicated thereafter. Patients will be evaluated for MRD negativity in the peripheral blood approximately every 3 months and with each bone marrow biopsy (other than the baseline biopsy). MRD testing will be performed by 4-color flow cytometry with a sensitivity of  $10^{-4}$  and when possible by next generation sequencing.

Patients who achieve CR or best response and are candidates for allogeneic transplant can elect to go off study to undergo transplant.

**Baseline Labs:**

- CBC with differential
- Comprehensive metabolic panel
- Amylase and lipase
- Testing to rule out active Hep B, Hep C, CMV and HIV infection
- Serum pregnancy test (pre-menopausal female patients only)
- FISH and karyotype cytogenetic analysis
- *IGHV* and *TP53* mutational status of all participants- Additional somatic mutation testing for *NOTCH1* and, *SF3B1* will be done for Dana-Farber CLL/SLL patients only.

**Instrumental Tests:**

- CT scans (or PET/CT scans for RS patients) prior to cycle 4, 7, and 13 and every 6 cycles thereafter at the investigator's discretion
- Bone marrow biopsy and aspirate prior to cycle 7, 13 and 25 and as clinically indicated thereafter
- MRD testing in the bone marrow prior to cycle 7, 13 and 25 and any time a clinically indicated bone marrow biopsy is performed thereafter
- MRD testing in the peripheral blood will occur approximately every 3 cycles during treatment up to Cycle 60, and every 6 cycles thereafter- This will also be tested approximately every 3 months during active follow up for routine disease monitoring

**Sample Size:**

We anticipate that approximately 12 CLL/SLL patients will be enrolled in the phase I study, using the traditional 3+3 design as described above.

CONFIDENTIAL

This document is confidential. Do not disclose or use except as authorized.

For the phase II study, a Simon's two-stage design will be employed with 12 CLL/SLL patients accrued to the first stage. All patients will be followed for up to one year. If at least 2 patients achieve a CR then an additional 23 patients will be accrued to the second stage. Patients who receive the MTD of venetoclax in the phase I portion of the trial can also be counted in the analysis of the phase II portion of the trial.

A separate cohort of 20 patients with Richter's Syndrome will be enrolled in parallel with the CLL/SLL cohort in a one stage design.

### **Key Eligibility Criteria (please see protocol section 3 for complete list):**

#### **Inclusion Criteria:**

- Must have a confirmed diagnosis of chronic lymphocytic leukemia or small lymphocytic lymphoma requiring therapy, as per IW-CLL 2008 criteria OR biopsy confirmed Richter's Syndrome (RS)
- Disease that has progressed during or relapsed after at least one previous CLL/SLL therapy (CLL/SLL patients only)
- ECOG performance status  $\leq 2$  (Karnofsky  $\geq 60\%$ , see Appendix A)
- Adequate hepatic function defined as:
  - Serum aspartate transaminase (AST) and alanine transaminase (ALT)  $\leq 3.0$  x upper limit of normal (ULN), bilirubin  $\leq 1.5$  x ULN (unless bilirubin rise is due to Gilbert's syndrome or of non-hepatic origin)
- Adequate renal function as defined by:
  - Serum creatinine  $\leq 1.5$  x ULN or creatinine clearance  $\geq 50$  mL/min using a 24-hour urine collection
- Patients must meet the following hematologic criteria at screening, unless they have significant bone marrow involvement of CLL confirmed on biopsy:
  - Absolute neutrophil count  $\geq 500$  cells/mm^3 ( $0.5 \times 10^9/L$ ). Growth factor is allowed in order to achieve this
  - Platelet count  $\geq 25,000$  cells/mm^3 ( $25 \times 10^9/L$ ) independent of transfusion within 7 days of screening

#### **Exclusion Criteria:**

- Previous treatment with venetoclax or duvelisib (prior venetoclax allowed for RS patients and for CLL/SLL patients if they have been off venetoclax therapy for at least one year prior to enrollment)
- Patients receiving cancer therapy (i.e., chemotherapy, radiation therapy, immunotherapy, biologic therapy, surgery) within 2 weeks of Cycle 1/Day 1 with the following exceptions:
  - For patients on targeted therapies, a washout of at least five half-lives is required
  - Patients who experience clinical deterioration may start therapy after a shorter

CONFIDENTIAL

This document is confidential. Do not disclose or use except as authorized.

washout period with prior approval by the PI

- Corticosteroid therapy (prednisone or equivalent  $\leq 20$  mg daily) is allowed
- Confirmed central nervous system involvement
- Allogeneic hematologic stem cell transplant within 6 months of starting study or active graft vs. host disease (GVHD) requiring treatment or prophylaxis
- Active malignancy other than CLL/SLL or Richter's Syndrome requiring ongoing therapy, with the exception of hormonal therapy
- Any active systemic infection requiring IV antibiotics or other uncontrolled, active infections
- Unable to receive prophylactic treatment for pneumocystis, herpes simplex virus (HSV), or herpes zoster (VZV) at screening
- Administration of live or live attenuated vaccine within 6 weeks of initiation of therapy
- Human immunodeficiency virus (HIV), hepatitis C virus (HCV), or hepatitis B virus (HBV)
- Major surgery within 4 weeks of first dose of study drug
- Currently active gastrointestinal disease, including colitis, inflammatory bowel disease and diarrhea requiring therapy
- Currently active, clinically significant cardiovascular disease, such as uncontrolled arrhythmia or Class 3 or 4 congestive heart failure as defined by the New York Heart Association Functional Classification; or a history of myocardial infarction, unstable angina, acute coronary syndrome, stroke, or sustained ventricular arrhythmia within 6 months prior to initiation of therapy
- Any life-threatening illness, medical condition, or organ system dysfunction that, in the investigator's opinion, could compromise the subject's safety
- Use of Coumadin for anticoagulation (other anticoagulants permitted)
- Concurrent administration of medications or foods that are strong inhibitors or inducers of CYP3A (see Appendix D)
- Ongoing treatment with chronic immunosuppressants (e.g., cyclosporine)
- History of chronic liver disease or veno-occlusive disease/sinusoidal obstruction syndrome
- History or concurrent condition of interstitial lung disease of any severity and/or severely impaired lung function
- Active abuse of alcohol or illicit drugs

**Intervention and Mode of Delivery:**

Duvelisib, 25 mg BID, oral

Venetoclax, up to 400 mg daily, oral

**Regulatory and Feasibility Issues:** Patients must have access to commercially available venetoclax. Secura Bio, Inc. will provide duvelisib at no cost to the participant.

CONFIDENTIAL

This document is confidential. Do not disclose or use except as authorized.

## 1. OBJECTIVES

### 1.1 Study Design

This is an open-label, multicenter, phase I/II study of duvelisib in combination with venetoclax for patients with relapsed/refractory CLL or SLL or Richter's Syndrome.

#### *Phase I*

The phase I portion of the trial will determine the dose, schedule, safety and tolerability of duvelisib in combination with venetoclax. Patients will start with 25 mg BID of duvelisib for seven days. A traditional 3 + 3 design will be used to accrue patients to one of three doses of venetoclax, which will start on day 8. The starting dose level of venetoclax will be 100 mg daily (dose level +1) with escalation to 200 mg daily (dose level +2) and to 400 mg daily (dose level +3). De-escalation to 50 mg daily (dose level -1) will be performed if unexpected toxicity is observed. At each dose level, patients start with 10 mg of venetoclax followed by a weekly dose ramp-up, with patients in the initial dosing cohorts stopping at a lower dose of venetoclax than the approved dose of 400 mg.

#### *Phase II*

The phase II study will occur in two stages in order to determine the rate of complete response (CR) of duvelisib in combination with the MTD of venetoclax. Patients will be treated with duvelisib plus venetoclax for up to one year followed by venetoclax monotherapy until the time of disease progression without clinical benefit, death, unacceptable toxicity, or withdrawal of consent.

Additionally, if after at least one year of treatment, a patient achieves a complete remission (CR) or complete remission with incomplete count recovery (CRi) with MRD-negativity in the bone marrow, they will have the option to discontinue therapy. Those that come off treatment for this reason will be monitored for disease recurrence with peripheral blood MRD testing by flow cytometry approximately every 3 months. Patients who have detectable recurrence (at minimum, confirmed by two successive peripheral blood MRD positive assessments) in the peripheral blood will have the option to restart venetoclax. If they do not achieve MRD negativity or have disease progression with venetoclax monotherapy after reaching full dose venetoclax, they have the option to add duvelisib and continue it until MRD negativity is achieved on two successive peripheral blood MRD assessments or indefinitely depending on tolerability.

Patients will be regularly monitored for minimal residual disease (MRD) throughout the trial.

### 1.2 Primary Objectives

#### *Phase I*

- Determine the dose limiting toxicities (DLT), maximum tolerated dose (MTD) as well as the recommended phase II dose and safety profile for this combination regimen of duvelisib plus venetoclax for patients with relapsed or refractory CLL/SLL

CONFIDENTIAL

This document is confidential. Do not disclose or use except as authorized.

*Phase II:*

- Determine the best rate of complete response (CR) or complete response with incomplete count recovery (CRi) of duvelisib in combination with the MTD of venetoclax as defined by the IWCLL 2008 criteria for CLL/SLL or Lugano 2014 criteria for RS.

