##### **11.3.1.2 Complete Response with incomplete marrow recovery (CRi):**

- Complete response as defined above, but without normal blood counts.

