***Phase II Study (CLL/SLL patients):***

***Treatment Efficacy***

The primary endpoint for the phase II study is the rate of complete response (CR) at 12 months according to 2008 IW-CLL criteria. The CR rate will be obtained for all patients at 12 months and will be reported as a percentage of total patients.

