### 13.2 Sample Size, Accrual Rate and Study Duration

We anticipate approximately 12 CLL/SLL patients will be enrolled in the phase I study, using the traditional 3+3 design as described above.

For the phase II study, a Simon two-stage design will be employed whereby a 10% complete response (CR) rate is considered not promising, a 30% complete response rate is considered promising, and the probabilities of a type I error (falsely accepting a non-promising therapy) and type II error (falsely rejecting a promising therapy) are set at 0.10 and 0.10, respectively. In the first stage of this design, 12 CLL/SLL patients will be accrued. All patients will be followed for up to one year. If at least 2 patients achieve CR then an additional 23 CLL/SLL patients will be accrued to the second stage. If 0 or 1 patients achieve CR the study will be terminated and declared negative. The probability of early stopping based on an optimal Simon’s two stage design is 65%. At the end of the trial, if 6 or more patients respond out of a total of 35 patients, then this combination will be considered worthy of further investigation. This design yields at least a 0.90 probability of a positive result if the true response rate is at least 30% and yields a 0.90 probability of a negative result if the true response rate is 10%.

Of note, all patients in the phase I study will be evaluated for response and can be counted in efficacy evaluations in stage 1 of the phase II portion of the trial. An exploratory analysis will also be performed to estimate the rate of CR with confidence intervals in the 29 patients treated at the venetoclax MTD.

For the Richter’s Syndrome Cohort, we plan to accrue 20 additional patients. Given the poor prognosis and lack of a standard of care for this population, we will not have an early stopping rule for this cohort based on efficacy or toxicity.

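### The CLL/SLL phase II primary endpoint is best CR or CRi in Section 1.2 but CR at 12 months in Section 13.1, and the synopsis and Section 13.2 disagree on which phase I patients count towards it

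*Combined protocol and SAP*

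**What the plan says.** **Endpoint.** Section 1.2, phase II: "Determine the best rate of complete response (CR) or complete response with incomplete count recovery (CRi"), by IWCLL 2008 for CLL/SLL, with no time point. Section 13.1, in its part on CLL/SLL, reads: "The primary endpoint for the phase II study is the rate of complete response (CR) at 12 months according to 2008 IW-CLL criteria".

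Elsewhere the plan speaks of CR and does not mention CRi:
- Schema, CLL/SLL Cohort: "If at least 2 CLL/SLL patients achieve a complete response (CR) as defined by the IWCLL 2008 criteria after one year", 23 more patients are enrolled.
- Synopsis, Primary Objectives: "Determine the rate of complete response (CR) of duvelisib in combination with the MTD of venetoclax".
- Synopsis, Study Design: the second stage opens if 2 patients "achieve a CR after one year of therapy, an additional 23 CLL/SLL patients will be enrolled in the second stage".
- Section 1.1: two stages "in order to determine the rate of complete response (CR) of duvelisib in combination with the MTD of venetoclax".
- Section 13.2: "a 10% complete response (CR) rate is considered not promising" and 30% is promising. Patients are followed for up to one year. The stage 1 rule counts CR, while the final rule counts patients who respond.

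Section 11.3.1.2 defines CRi as "Complete response as defined above, but without normal blood counts".

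**Patients.** The synopsis (Sample Size) allows phase I patients who receive the MTD to be counted in the phase II analysis. Section 13.2 allows all phase I patients to be counted in stage 1, and adds an exploratory CR estimate in 29 patients treated at the MTD.

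**The concern.** The two statements of the primary endpoint differ in two ways.

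- **Category.** A CRi fails the blood-count criteria for CR in Section 11.3.1.1. It counts under Section 1.2 but not under the wording of Section 13.1.
- **Timing.** A CR needs a marrow sample, and marrows are mandatory at C7D1, C13D1 and C25D1 (Section 5). A CR first documented at C25D1 counts under Section 1.2 but not as CR at 12 months. The same holds for a CR seen at C7D1 and lost by C13D1.

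This endpoint drives both decisions of the Simon design. If the choice is still open when the data are seen, the stated error rates do not protect either decision.

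The patient question adds to this. The objective concerns the MTD, yet Section 13.2 admits patients from lower dose levels to the stage 1 count, and so to the final count.

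**Working it through.** **Inputs (Section 13.2).** Null rate 0.10, target rate 0.30, alpha and beta 0.10. Stage 1 has 12 patients and stops at 1 CR or fewer. Stage 2 adds 23 patients, and the result is positive at 6 or more of 35.

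**1. The plan's own figures.**

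P(early stop) = (1−p)^12 + 12p(1−p)^11. At p = 0.10 this is 0.282 + 0.377 = 0.659 (plan: 65%).

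P(positive) = Σ over x = 2 to 12 of P(X1 = x) × P(X2 ≥ 6−x), with X1 ~ Bin(12, p) and X2 ~ Bin(23, p).
- p = 0.10: 0.098, so P(negative) = 0.902 (plan: 0.90).
- p = 0.30: 0.901 (plan: at least 0.90).

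The figures reproduce. The conflict is one of definition, not of arithmetic.

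**2. Same data, two decisions.**

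| Data | Best CR or CRi (1.2) | CR (13.1) |
|---|---|---|
| 1 CR + 1 CRi in 12 | 2: open stage 2 | 1: stop |
| 5 CR + 1 CRi in 35 | 6: positive | 5: negative |

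The second row assumes that stage 1 was passed under both definitions.

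**3. Size, under assumed rates.** The documents give no CRi rate and do not say whether 10% and 30% include CRi. Both directions are therefore shown, with the formula in step 1.

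*10% refers to CR only, and the broader endpoint raises the uninteresting rate:*

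| Rate on broader endpoint | P(early stop) | P(positive) |
|---|---|---|
| 0.10 (no change) | 0.659 | 0.098 |
| 0.12 | 0.569 | 0.180 |
| 0.15 | 0.444 | 0.337 |

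Every CR is also a CR or CRi, so the probability that the two definitions disagree is a simple difference. At the gate it is 0.659 − 0.569 = 0.090 or 0.659 − 0.444 = 0.215. On the final call it is 0.180 − 0.098 = 0.082 or 0.337 − 0.098 = 0.239.

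*10% and 30% already include CRi, and CR alone is 8% and 25%:* P(positive) on CR alone is 0.042 at 8% and 0.79 at 25%. Counting CR alone is then conservative and loses power.

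**4. Phase I patients in stage 1.** The figure of 29 leaves 35 − 29 = 6 patients not at the MTD, which matches 6 + 23 = 29. Let X1 be Bin(6, q) + Bin(6, 0.30), where q is the CR rate below the MTD, and let stage 2 be at 0.30.

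For q = 0.10:
- P(X1 = 0) = 0.9^6 × 0.7^6 = 0.5314 × 0.1176 = 0.0625.
- P(X1 = 1) = 0.3543 × 0.1176 + 0.5314 × 0.3025 = 0.2025.
- P(early stop) = 0.265.

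| Assumed CR rate in the six | P(early stop) | Power |
|---|---|---|
| 0.30 (same as MTD) | 0.085 | 0.901 |
| 0.20 | 0.156 | 0.826 |
| 0.10 | 0.265 | 0.715 |

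Under the null, with 10% at the MTD and the six at 5%, P(positive) is 0.058. With the six also at 10% it is 0.098. Type I error is not inflated.

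**The case against.** **CR may be shorthand for CR/CRi.** None of the CR-only places excludes CRi in words. Section 13.3 defines ORR to include CRi and then restates it as complete and partial response. Section 11.3.1.8 classes patients without CR, PR or progression as stable, which on a strict reading leaves CRi with no response category. This stands as a reason not to treat the intent as settled. It does not remove the conflict: Section 1.2 names CRi separately, Section 11.3.1.2 defines it separately, and the difference in timing remains.

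**Section 1.2 may be the newer text.** A reader might infer from the count of places that Section 1.2 is simply out of date. The documents do not show that. Section 1.3 adds two-year MRD and best MRD-negative CR/CRi, which fits the mandatory C25D1 marrow, while the synopsis and Section 13.3 stop at one year. So Section 13 could be the part left behind. Either way one side must change.

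**The patient rules are permissive.** Both places say that phase I patients can be counted, and patients at lower dose levels may escalate to the MTD (Sections 5 and 5.1.2.1). On one reading those who escalate have received the MTD. That shrinks the power loss, and it is itself a reason to define the set.

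**The sizes are assumed.** True. The documents give neither a CRi rate nor a CR rate by dose. The reversals in step 2 need no such assumption.

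**Conclusion.** The contradiction is real, and nothing in the documents resolves it. The Simon figures are correct for the endpoint to which 10% and 30% refer. As written, two primary readings can reverse both the stage 1 and the final decision on the same data. This must be fixed.

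The size depends on assumed rates. On the broader endpoint the chance of a false positive would be 0.18 or 0.34 if the uninteresting rate were 12% or 15%. In the opposite case, CR alone would give 0.042 and power 0.79. A reader might infer that the type I error is inflated, but the documents do not support any one direction.

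On patients, the loss is one of power: 0.72 or 0.83 instead of 0.90 if six stage 1 patients have a CR rate of 10% or 20% against 30% at the MTD and do not escalate.

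A reader might also infer from the three extra MTD patients in Section 5 that 9 of the 12 stage 1 patients are at the MTD. Six below the MTD plus nine at it make 15, and no rule says which three would be dropped, so no figure here rests on that.

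**What to change.** **Endpoint.** State one CLL/SLL primary endpoint and use it in Sections 1.2, 13.1 and 13.2. The default that needs no redesign is CR at 12 months as in Section 13.1, based on the C13D1 restaging, with best CR/CRi listed as secondary and given a 95% confidence interval. If the sponsor intends best CR/CRi, Sections 13.1 and 13.2 must change, and the 10% and 30% rates must be justified, or the boundaries recomputed, on that endpoint. In the final decision rule of Section 13.2, name the chosen endpoint in place of the word respond.

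**Patients.** Reconcile the synopsis with Section 13.2. Base the primary stage 1 and final counts on patients assigned to the MTD, say how patients who later escalate to it are handled, and report the other phase I patients separately. Correct the figure of 29: with all counted patients at the MTD it becomes 12 + 23 = 35.

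**If stage 1 has already been assessed,** keep both the endpoint and the patient set used then, disclose them, and report the alternative as a sensitivity analysis.

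**Cost.** Mainly wording. The reported CR rate may be slightly lower than with best CR/CRi. Some stage 1 places go to phase II patients (12 − 6 = 6 if six phase I patients are at the MTD), within the 12 that the schema already plans.
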